Important note (3)	
A key point will be to understand the contribution of each of the drugs in generating toxicities. To this purpose, the CMC will specifically investigate whether observed toxicities relate to overlapping effects (such as fatigue, nausea diarrhea) or specific toxicities (such as febrile neutropenia – palbociclib) or low platelets level (axitinib). Appendix 8 describes all observed toxicities and outlines common or specific toxicities. Main toxicities specific to each drug are summarized in Important note (5).
 
Rules in case of toxicity/dose modifications:
 
For any Grade 3 dose-limiting toxicity (see page 32 for dose-limiting toxicity definitions) that is deemed to be drug specific, that drug will be held until resolution to <Grade 1. The drug will then be restarted with the dose at the next lowest level. If Grade 3 or greater toxicity recurs, the drug will be permanently stopped. Exception is hematologic toxicity which may be handled as in Important note (5), palbociclib section or Important note (6).
 
If a toxicity has been deemed to be due to a single drug, but persists at <math>\geq</math> grade 3 level after stopping the drug, all drugs will be stopped.
 
If it is unclear as to the drug that is causing a toxicity, all three drugs will be held.

	
Toxicities that may be clearly attributable to avelumab include immune toxicities such as immune mediated pneumonitis, hepatitis, colitis and nephritis, and infusion related reactions.
 
Toxicities clearly attributable to axitinib include hypertension and proteinuria.
 
Toxicities clearly attributable to palbociclib include lowering of white blood cells (WBC) or platelet counts.
 
For Grade 4 dose limiting toxicities, the drug to which it is attributable will be permanently stopped. If it is not clear as to which drug is associated with the toxicity, all drugs will be permanently stopped.
 
A Clinical Monitoring Committee (that includes site PIs) may be convened to help decide to which drug the toxicity is attributable.

Important note (4)	For dose interruption and reduction events, accurate medical administration records will be maintained to capture changes in dosing regimens, including concomitant medications.

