7. Discontinue axitinib in patients developing Reversible Posterior Leukoencephalopathy Syndrome (RPLS). RPLS is a neurological disorder which can present with headache, seizure, lethargy, confusion, blindness and other visual and neurologic disturbances. Mild to severe hypertension may be present. Magnetic resonance imaging is necessary to confirm the diagnosis of RPLS. The safety of reinitiating axitinib therapy in patients previously experiencing RPLS is not known.
8. Monitoring for proteinuria before initiation of, and periodically throughout, treatment with axitinib is recommended. For patients who develop moderate to severe proteinuria, reduce the dose or temporarily interrupt axitinib treatment.
9. Monitor ALT, aspartate aminotransferase (AST) and bilirubin before initiation of and periodically throughout treatment with axitinib.
10. Monitor for cavitation apparition throughout the treatment with axitinib.

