**Recurrent Grade 3 ADRs and Grade 3 infusion-related reaction require permanent discontinuation.**

**Any Grade 2 ADR should be managed as follows:**

- If a Grade 2 ADR resolves to Grade  $\leq$  1 by the last day of the current cycle, treatment may continue.
- If a Grade 2 ADR does not resolve to Grade  $\leq$  1 by the last day of the current cycle, infusions should not be given on the following cycle. If at the end of the following cycle the event has not resolved to Grade 1, it should be treated as a Grade 3 or 4 (except for hormone insufficiencies, that can be managed by replacement therapy; for these hormone insufficiencies, up to 2 subsequent doses may be omitted).
- Upon the second occurrence of the same Grade 2 ADR (except for hormone insufficiencies that can be managed by replacement therapy) in the same subject, treatment with avelumab has to be permanently discontinued.

Important note (6):	Specific protocol dose modification for toxicity management related to palbociclib: 

- In case of recurrent grade 3 hematologic toxicities, palbociclib may be reduced to 75 mg po daily one week off and one week on.

- In case of other severe (<math>\geq</math> grade 3) toxicity related to palbociclib, consider holding palbociclib until toxicity is grade 1 or less, then resume at the alternate schedule of 2 weeks OFF / 2 weeks ON.

----------------------------	---

- **DLT will be defined as:**

Any of the following events that are considered to be clinically significant and meaningful as per evaluation of the attending physicians and confirmed by CMC and at least possibly related to drug. DLTs for the purposes of dose-escalation will be evaluated during the 28-day period following the first dose of study treatment. Each treatment cycle is four weeks. Toxicities will be graded and documented according the NCI CTCAE (v4.03).

- **Non-hematological dose-limiting toxicity is defined as:**

- Persistent Grade 3 or 4 hypertension despite treatment with anti-hypertensive drugs.
- Grade 3 or 4 Gastrointestinal bleeding.
- Grade 3 or 4 Gastrointestinal perforation or fistula.
- Development of Reversible Posterior Leukoencephalopathy Syndrome.
- Persistent Grade 3 or 4 proteinuria.
- Grade 3 or 4 arterial or venous thromboembolic events.

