Uveitis	X	-	-	Specific	0.1% to 0.99%
Posterior reversible encephalopathy syndrome	-	X	-	Specific	0.1% to 0.99%
Dry skin	-	X	X	Common to 2	More than 10%
Dyspepsia (indigestion)	-	X	X	Common to 2	More than 10%
Stomatitis (inflammation of the mouth)	-	X	X	Common to 2	More than 10%
Pyrexia (fever)	X	-	X	Common to 2	More than 10% for Avelumab, 1% to 10% for Palbociclib
Back pain	X	-	X	Common to 2	More than 10% for Avelumab, 1% to 10% for Palbociclib
Oedema peripheral	X	-	X	Common to 2	More than 10% for Avelumab, 1% to 10% for Palbociclib
Dysgeusia (change of sense of taste)	-	X	X	Common to 2	More than 10% for Axitinib, 1% to 10% for Palbociclib
Mucosal inflammation		X	X	Common to 2	More than 10% for Axitinib, 1% to 10% for Palbociclib
Pain in extremity	-	X	X	Common to 2	More than 10% for Axitinib, 1% to 10% for Palbociclib
Chills	X	-	X	Common to 2	1% to 10% for Palbociclib and Avelumab
Blood creatinine increased	-	X	X	Common to 2	1% to 10% for Axitinib, more than 10% for Palbocyclib
Hypothyroidism	X	X	-	Common to 2	1% to 10% for Avelumab, more than 10% for Axitinib
Neutropenia	-	X	X	Common to 2	0.1% to 0.99% for Axitinib, more than 10% for Palbocyclib
Alanine aminotransferase increased	X	X	-	Common to 2	0.1% to 0.99% for avelumab, 1% to 10% for axitinib
Hyperthyroidism	X	X	-	Common to 2	1% to 10% for axitinib, 0.1% to 0.99% for avelumab
Hypokalaemia	X	X	-	Common to 2	1% to 10%

Adverse Events	Avelumab	Axitinib	Palbociclib	Specificity	Frequency
Lipase and amylase increased	X	X	-	Common to 2	1% to 10%
Alopecia (hair loss)	-	X	X	Common to 2	1% to 10%
Dizziness	-	X	X	Common to 2	1% to 10%
Flatulence	-	X	X	Common to 2	1% to 10%
Oropharyngeal pain	-	X	X	Common to 2	1% to 10%
Constipation	X	X	X	Common to 3	More than 10%
Diarrhoea	X	X	X	Common to 3	More than 10%
Decreased appetite	X	X	X	Common to 3	More than 10%
Fatigue	X	X	X	Common to 3	More than 10%
Nausea	X	X	X	Common to 3	More than 10%
Vomiting	X	X	X	Common to 3	More than 10%
Weight decreased	X	X	X	Common to 3	More than 10% for Avelumab, 1% to 10% for Axitinib and Palbociclib
Anaemia	X	X	X	Common to 3	More than 10% for Avelumab and Palbociclib, 1% to 10% for Axitinib
Abdominal pain	X	X	X	Common to 3	More than 10% for Avelumab and Axitinib, 1% to 10% for Palbociclib
Cough	X	X	X	Common to 3	More than 10% for Avelumab and Axitinib, 1% to 10% for Palbociclib
Dyspnoea (shortness of breath)	X	X	X	Common to 3	More than 10% for Avelumab and Axitinib, 1% to 10% for Palbociclib

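### The dose-modification rules conflict on axitinib after Grade 3 RPLS and on recurrence of Grade 3 or worse toxicity, and no text says which rule governs

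*Combined protocol and SAP*

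**What the plan says.** Dose changes after toxicity are governed from several places in Section 3.3.1.

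- **Important note (3), Grade 3.** A drug held for a drug-specific Grade 3 DLT comes back once the event has resolved to below Grade 1: "The drug will then be restarted with the dose at the next lowest level". On recurrence: "If Grade 3 or greater toxicity recurs, the drug will be permanently stopped". The one stated exception is hematologic toxicity, which is sent to the palbociclib part of note (5) or to note (6).
- **Important note (3), Grade 4.** "For Grade 4 dose limiting toxicities, the drug to which it is attributable will be permanently stopped". Where the cause is uncertain: "If it is not clear as to which drug is associated with the toxicity, all drugs will be permanently stopped".
- **DLT list.** The non-hematological DLTs include, with no grade attached, "Development of Reversible Posterior Leukoencephalopathy Syndrome".
- **Important note (5), axitinib toxicity management, item 7.** "Discontinue axitinib in patients developing Reversible Posterior Leukoencephalopathy Syndrome (RPLS"), followed by the warning: "The safety of reinitiating axitinib therapy in patients previously experiencing RPLS is not known".
- **Dose reduction paragraph, end of Section 3.3.1.** After a DLT of unclear cause, drugs may restart one level lower. If one drug is judged responsible, only that drug may need reducing. A second such reduction is allowed if toxicity recurs. None of these permissions carries a grade limit. Responders may be reduced further.

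Appendix 8 lists "Posterior reversible encephalopathy syndrome" as specific to axitinib.

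**The concern.** These are instructions on whether a patient is given a drug again after serious harm. A site that follows note (3) literally would re-expose a patient to axitinib after Grade 3 RPLS, although the same section says to discontinue and warns that the safety of restarting is unknown. After a recurrent Grade 3 non-hematologic toxicity, one investigator could stop the drug and another could reduce it a second time, each with protocol text in support. Apart from the hematologic exception, no text ranks note (3), note (5) and the Dose reduction paragraph. What is at stake is patient safety and uniform conduct across centers. The statistical design is not affected.

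**Working it through.** The plan gives no figure to reproduce here, so the check sets the rules side by side.

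| Situation | Important note (3) | Other text | Result |
|---|---|---|---|
| Grade 3 RPLS, axitinib specific | Hold, then restart one level lower | Note (5), axitinib item 7: discontinue | Conflict |
| Non-hematologic toxicity recurring at Grade 3 or above | Permanent stop | Dose reduction paragraph: second reduction allowed, no grade limit | Conflict |
| Grade 4 DLT, cause unclear | All drugs stopped permanently | Dose reduction paragraph: may restart lower, no grade limit | Precedence unstated |
| Grade 4 DLT, cause known | That drug stopped permanently | Dose reduction paragraph: that drug may need reducing, no grade limit | Precedence unstated |
| Grade 4 GI bleeding attributed to axitinib | Permanent stop | Note (5) and the safety assessments in 3.3.1 and 5.4: temporary interruption if bleeding needs intervention | Precedence unstated |
| Grade 4 persistent hypertension attributed to axitinib | Permanent stop | Note (5): reduce first; discontinue if still severe after reduction; consider discontinuing in hypertensive crisis | Precedence unstated |

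**Why the first row is a conflict.** The restart instruction applies if the RPLS event is confirmed as a DLT, is graded 3, is deemed axitinib specific and has resolved. RPLS is on the DLT list, and Appendix 8 supports the attribution. Once those conditions are met, note (3)'s restart is worded as mandatory, and RPLS is not among its exceptions.

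**Why the second row is a conflict.** Below Grade 3 the two texts agree. At Grade 3 or above, a permission to reduce cannot stand beside a required permanent stop.

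**Why the other rows are weaker.** For uncertain attribution below Grade 4, note (3) holds all three drugs and gives no restart rule. The Dose reduction paragraph can be read as supplying one, and likewise as covering only the lower grades when the cause is known. Interruption for bleeding can be the immediate step before a permanent stop. Reducing for hypertension can be read as guidance for cases short of a Grade 4 DLT. Each reading is reasonable, but none is written down.

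**Other listed DLTs.** GI perforation or fistula and thromboembolic events have no axitinib dose action in note (5), so they do not clash. For proteinuria, note (5) describes severity in words without a grade, so no clash is shown.

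**Scale of the RPLS case.** Inputs: a frequency of 0.1% to 0.99% (Appendix 8, single-agent axitinib), and about 30 patients treated in phase 1 plus up to 100 in phase 2 (Section 1.2.1). Expected cases = N × p; chance of at least one = 1 − (1 − p)^N.

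- N = 30: 30 × 0.001 = 0.03 to 30 × 0.0099 = 0.30 cases; chance 1 − 0.999^30 = 3% to 1 − 0.9901^30 = 26%.
- N = 130: 130 × 0.001 = 0.13 to 130 × 0.0099 = 1.29 cases; chance 1 − 0.999^130 = 12% to 1 − 0.9901^130 = 73%.

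The spread mostly reflects the width of the frequency band. The figures cover RPLS of any grade, so they do not estimate how often the Grade 3 conflict would arise.

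**The case against.** The best defense is that a specific instruction overrides a general one. Note (5) has a single, plain RPLS instruction, and note (3) itself points to note (5) for drug-specific toxicities. Many investigators would discontinue axitinib without hesitation. There are safeguards too: the listed DLTs must be confirmed by the Clinical Monitoring Committee (CMC), which meets at least monthly on toxicity, and under Section 5.7 the treating physician can withdraw a patient whose best interest requires it.

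These points lower the risk, and they count against any inference that sites would diverge unchecked. They do not settle the text. Note (3) names the one category it hands over to another note, and RPLS is not in it. Note (3) labels its content as rules, while note (5) describes its own as guidance. No text gives the CMC the choice between conflicting instructions.

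A reader might also infer that the Grade 4 rows are outright contradictions. The documents do not support that, because the reconciling readings above are open. The responder allowance is likewise an explicit special provision, so it should be kept and named as an exception.

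**Conclusion.** The point holds as a patient-safety defect in the wording. There are two clear conflicts (Grade 3 RPLS attributed to axitinib; non-hematologic toxicity recurring at Grade 3 or above) and four Grade 4 situations where precedence is unstated but can be reconciled. It should be corrected by amendment.

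Two stronger readings are not supported. First, a reader might infer that no single precedence rule could resolve everything. Ranking the notes does fail: note (3) first restarts axitinib after Grade 3 RPLS, and note (5) first leaves Grade 4 bleeding open. But a rule that the more restrictive instruction applies settles every row of the table; the protocol simply does not state it. Second, the RPLS figures are not upper limits for this trial. The rate is for axitinib alone, and note (5) warns that palbociclib may raise axitinib exposure. Neither the combination rate nor the Grade 3 share is given.

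The conclusion assumes that the syndrome named in Appendix 8 is the same event as RPLS. The N = 130 figures also assume that the Section 3.3.1 rules carry into phase 2, for which Section 3.3.2 gives no separate dose-modification rules. DLT counts, toxicity boundaries, sample size and power are unchanged.

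**What to change.** Add to Important note (3): *Where dose-modification instructions differ, the more restrictive applies, except that hematologic toxicity attributable to palbociclib follows note (5), palbociclib section, and note (6). RPLS of any grade: permanently discontinue axitinib, no restart.* The hematologic exception must be explicit at Grade 4 as well, because note (3) places its present exception in the Grade 3 paragraph while the palbociclib section resumes treatment after Grade 4.

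In the Dose reduction paragraph:

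- limit restart or reduction after a non-hematologic DLT, of known or unclear cause, to Grade 3 or lower;
- limit the second reduction for non-hematologic toxicity to recurrence below Grade 3;
- keep the responder allowance as it now stands, named as an exception to the stop on recurrence and to the more-restrictive rule, but never after RPLS.

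The cost is amendment wording and a site memo. Investigators lose some discretion after Grade 4 DLTs and on recurrence at Grade 3 or above. No patients or procedures are added.

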### **ADVERSE DRUG REACTIONS REQUIRING AVELUMAB DISCONTINUATION OR MODIFICATION**

Dose escalation or reduction is not recommended. Dosing delay or discontinuation may be required based on individual safety and tolerability ([refer to Appendix 6](#)). Resume avelumab in patients whose adverse reactions recover to Grade 1 or resolved.

**Any Grade 4 ADRs require permanent treatment discontinuation with avelumab** except for single laboratory values out of normal range that are unlikely related to study treatment as assessed by the Investigator, do not have any clinical correlate, and resolve within 7 days with adequate medical management and endocrinopathies controlled with hormone replacement.

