Patients who have a dose limiting toxicity and it is unclear as to which drug may have caused the toxicity, may restart drugs at the next lower dose level once toxicity returns to  $\leq$  Grade I. If the investigator deems the toxicity to be due to one of the drugs in the regimen, only that drug may need to be reduced to the next lower dose level. A second dose reduction of this type may occur if toxicity recurs. For a patient who is responding (PR or CR) the investigator may continue to reduce the dose to the lowest dose level tolerable; for these responding patients, if one drug is deemed responsible for recurring serious toxicity, it may be stopped and the other two drugs continued after review by the clinical monitoring committee.

### 3.3.2. The Phase 2

When the recommended Phase 2 dose is reached, there will be a first expansion of the study to explore efficacy of the tested triple combination. In the expansion, only patients with unresectable or metastatic NSCLC with no prior treatment line will be treated. Up to 100 patients will be treated with the combination (~120 patients enrolled\*) until progression. For ethical reasons, even patients who failed biopsy(ies) will be treated with the triple-therapy. Pending clinical activity, the study may be extended (with a study amendment) to an additional 100 patients treated in phase 2 in order to attain sufficient statistical power to support the validity of the approach.

Study participation will be offered to patients with locally advanced or metastatic disease. Patients with documented oncogenic aberrations (EGFR, ALK, ROS1 if available, MET exon 14 skipping if available) at enrollment will be excluded from the trial. In the case of patients already treated on SPRING protocol who are later determined to have EGFR mutation or ALK translocation or ROS1 or MET exon 14 skipping mutations after SIMS analyses, they will be asked to re-consent. Patients will be included in the study regardless of their PD1 or PD-L1 expression status. Main outcome variables will include response rate (RR), progression-free survival (PFS), and overall survival (OS).

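### Section 3.3.1 gives two conflicting dose-modification rules, for recurrent Grade 3 or greater toxicity and for Grade 4 DLTs, and does not say which governs.

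*Combined protocol and SAP*

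**What the plan says.** Both rules are in section 3.3.1.

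**Important note (3).** After a Grade 3 DLT judged specific to one drug, that drug is held and then restarted one dose lower. On recurrence: "If Grade 3 or greater toxicity recurs, the drug will be permanently stopped". The one stated exception is in the same paragraph: "Exception is hematologic toxicity which may be handled as in" the palbociclib part of note (5) or note (6). After a Grade 4 DLT the responsible drug is stopped for good, and "If it is not clear as to which drug is associated with the toxicity, all drugs will be permanently stopped".

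**Dose reduction paragraph.** After a DLT of unclear cause, patients "may restart drugs at the next lower dose level once toxicity returns to" Grade 1 or lower. If one drug is held responsible, only that drug may need lowering. Then: "A second dose reduction of this type may occur if toxicity recurs". Responders have a wider allowance: "For a patient who is responding (PR or CR) the investigator may continue to reduce the dose to the lowest dose level tolerable". If one drug causes recurring serious toxicity in a responder, "it may be stopped and the other two drugs continued after review by the clinical monitoring committee". No grade limit appears anywhere in this paragraph.

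**Avelumab.** Its own rules in section 3.3.1 advise against dose reduction, require permanent discontinuation for recurrent Grade 3 reactions, and state: "Any Grade 4 ADRs require permanent treatment discontinuation with avelumab", with narrow exceptions.

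**The concern.** A dose-modification rule should give one answer for one event. Here note (3) takes the patient off a drug, or off all three, where the Dose reduction paragraph lets the investigator go on dosing. Two sites could treat the same severe event differently, each with protocol text in support, and the site that re-doses would breach note (3).

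The unclear-cause case is foreseeable. Note (3) itself names fatigue, nausea and diarrhea as overlapping effects, and Appendix 8 lists diarrhea as common to all three drugs. The DLT definition exempts Grade 3 diarrhea that responds to supportive treatment within the stated time, but not Grade 4. Section 3.3.2 gives no dose-modification rules of its own, so the same text presumably also applies to the phase 2 cohort of up to 100 treated patients.

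**Working it through.** The plan gives no figure to reproduce. The check sets the two rules side by side.

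| Event | Note (3) | Dose reduction paragraph | Compatible? |
|---|---|---|---|
| Recurrent non-hematologic Grade 3 or greater toxicity, one drug responsible | Permanent stop after one reduction | Second reduction permitted | No |
| Grade 4 DLT, drug known | Permanent stop of that drug | That drug may be reduced | No |
| Grade 4 DLT, drug unclear | Permanent stop of all drugs | Restart one level lower | No |
| Grade 3 DLT, drug unclear | Hold all three; no permanent-stop rule on recurrence | Restart one level lower; second reduction permitted | Yes |

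**Does the Dose reduction paragraph reach Grade 4?** Yes. It applies to patients with a DLT, and the DLT definition lists Grade 4 events, for example Grade 3 or 4 gastrointestinal bleeding.

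**Do drug-specific rules settle it?** In part.

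- Avelumab: largely settled, since its own rules agree with note (3).
- Axitinib: note (5) already calls for discontinuation for severe hypertension that persists despite treatment and dose reduction, and for reversible posterior leukoencephalopathy syndrome. Its proteinuria advice (reduce or interrupt) does not address recurrence.
- Palbociclib: recurrent hematologic toxicity is excepted from note (3). For other toxicity of Grade 3 or higher, note (6) suggests holding the drug and resuming on an alternate schedule, without excluding Grade 4 or recurrence.

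**A related gap inside note (3).** The hematologic exception is in the Grade 3 paragraph only. Grade 4 neutropenia lasting more than 7 days is a DLT, so note (3) requires a permanent stop. The palbociclib part of note (5) resumes the drug one dose lower after Grade 4 hematologic toxicity.

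**Is there room to reduce?** Doses in the Treatment Plan at levels -1, 1, 2, 3 and 4:

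- Axitinib: 2, 3, 5, 5, 5 mg twice daily. Two reductions (5 to 3 to 2) are possible from levels 2, 3 and 4.
- Palbociclib: 75, 75, 75, 100, 125 mg. Two reductions (125 to 100 to 75) are possible from level 4 only.
- Avelumab: 10 mg/kg at every level.

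If the next lower dose level means the next level in this table, each step down lowers one drug: 4 to 3 and 3 to 2 lower palbociclib, 2 to 1 and 1 to -1 lower axitinib. A restart after a DLT of unclear cause would then give the other two drugs at an unchanged dose, apart from any separate avelumab stop. So the permission can be used in practice. These counts do not show how often it would be used.

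**The case against.** **The mandatory wording prevails, so a site simply stops.** Stopping does satisfy both texts. The second reduction would still have a use for recurrence below Grade 3, for hematologic toxicity and for Grade 3 toxicity of unclear cause. This is a sensible reading, but the protocol does not state it. It does not resolve the Grade 4 cases, and it fits poorly with the responder clause, which makes stopping optional for recurring serious toxicity.

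**The responder clause is a deliberate exception.** It reads that way, and it requires CMC review before one drug is stopped and the other two continued. Note (3) does not recognize it.

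**The CMC is already involved.** This stands in part. A reader might infer that a site could re-dose after a DLT with no CMC involvement. The documents do not support that: the DLT definition requires CMC confirmation, and note (3) allows the CMC to be convened on attribution. What remains is narrower. Confirming that an event is a DLT is not approving a restart, and the Dose reduction paragraph asks for no further review before a restart or a second reduction.

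**The scope is narrow.** This also stands. The avelumab rules, the two axitinib rules and the hematologic exception remove several cases.

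**Conclusion.** The conflict is real and should be fixed. It covers recurrent non-hematologic Grade 3 or greater toxicity attributed to axitinib or palbociclib, and Grade 4 DLTs whether the responsible drug is known or not. No text says which rule governs.

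Its frequency cannot be stated, because the documents give no rate for either event. It is an operational and safety inconsistency and leaves sample size, power and stopping boundaries unchanged.

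Two stronger conclusions might be drawn, and neither is supported. The dose-level counts do not measure how many patients are affected: they show only that a lower dose exists, and patients are not spread evenly over the levels. Nor does note (3) forbid every second reduction after recurrent Grade 3 toxicity. Its recurrence rule covers drug-specific toxicity, so recurrent Grade 3 toxicity of unclear cause is not in conflict.

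The verdict assumes that the Dose reduction paragraph, which states no grade limit, means what it says.

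**What to change.** The edits below take note (3), the stricter rule, as the default. The sponsor should confirm that choice.

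1. In the Dose reduction paragraph, state that it is subject to note (3).
2. Limit its restart and reduction after a DLT to DLTs below Grade 4, except palbociclib hematologic toxicity handled under notes (5) and (6). The limit should be below Grade 4, not Grade 3 only, because Grade 2 pneumonitis is also a DLT.
3. State that the second reduction does not apply to recurrent drug-specific non-hematologic toxicity of Grade 3 or greater. Leave recurrent Grade 3 toxicity of unclear cause as it is.
4. If the responder allowance is intended, write it into note (3) as an explicit exception with CMC review, excluding avelumab and Grade 4 events.
5. For consistency, extend note (3)'s hematologic exception to its Grade 4 paragraph, and limit note (6)'s resumption after other palbociclib toxicity to a first Grade 3 occurrence. Limiting it to Grade 3 alone would leave the recurrence conflict open.

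The cost is protocol wording in notes (3) and (6) and the Dose reduction paragraph. Note (5) can stay as it is. No analysis or sample size changes.
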